# 4.3.2.4 Assessment of Compliance

Accountability will be assessed by maintaining adequate drug preparation and dispensing records. A call for drug administration to the interactive web–based response system (IWRS) will also be used to assess compliance.

# 4.3.3 Premedication for Infusion-Related Reactions with Antihistamines, Anti-Pyretics, and Methylprednisolone

## 4.3.3.1 Antihistamines and Anti-Pyretics

During the controlled treatment periods of Studies WA21092 and WA21093, the addition of oral antihistamine to methylprednisolone pretreatment for each dose was associated with at least a 2-fold lower incidence in infusion reactions compared with pretreatment with methylprednisolone alone. Therefore, all patients will receive mandatory prophylactic treatment with an antihistamine drug (e.g., diphenhydramine) approximately 30–60 minutes before each infusion of ocrelizumab to further reduce the frequency and severity of IRRs.

The addition of an analgesic/antipyretic (e.g., acetaminophen/paracetamol) may also be considered.

Patients administered a sedating antihistamine for the treatment or prevention of infusion reactions should be given appropriate warnings concerning drowsiness and potential impairment of ability to drive or operate machinery.

Since transient hypotension may occur during ocrelizumab infusion, patients with low blood pressure should be monitored carefully.

# 4.3.3.2 Methylprednisolone

All patients will also receive mandatory prophylactic treatment with methylprednisolone, administered by slow IV infusion to be completed approximately 30 minutes before the start of each ocrelizumab infusion. In the event that the use of methylprednisolone is

#### Ocrelizumab—F. Hoffmann-La Roche Ltd

59/Protocol WA39085, Version 10

contraindicated, an equivalent dose of alternative steroid should be used as premedication prior to the infusion.

The dose recommendation for slow IV infusion of methylprednisolone is as follows: dose adjusted to weight for patients <40 kg (2 mg/kg) and for patients  $\ge 40$  kg (100 mg).

# 4.3.4 Managing Infusion-Related Reactions

## 4.3.4.1 Treatment of IRRs

IRRs should be treated symptomatically with oral acetaminophen/paracetamol, and intramuscular or slow IV antihistamine administration, such as diphenhydramine, both according to labeled age-related doses. Acetaminophen/paracetamol and antihistamine administration should be repeated as clinically indicated. Non–allergic events should be treated symptomatically as judged clinically relevant by the investigator.

In patients with associated respiratory symptoms (stridor, wheeze, or bronchospasm), additional treatment with bronchodilators may be indicated.

Physicians should monitor patients with a history of asthma carefully and institute an appropriate treatment if signs and symptoms of asthma are noticed.

Note: As an IRR can occur within 24 hours of an infusion, a structured telephone interview will be conducted by site personnel 24  $(\pm 4)$  hours after each infusion to identify and collect information on any changes in the patient's health status (i.e., any unusual signs or symptoms since they left the clinic after the infusion) (see Appendix 4).

#### 4.3.4.2 Infusion-Rate Modifications and Interruptions for Infusion–Related Reactions

Slowing of the infusion rate or interruption of the infusion may be necessary in the event of an IRR. In rare cases, ocrelizumab treatment may need to be discontinued. Guidance is provided below.

Handling of IRRs will depend on the intensity of symptoms (see Section 5.3.3 for severity grading scale of IRRs).

### Mild-to-Moderate Infusion-Related Reactions

In the event that a patient experiences mild or moderate (Grade 1 or 2) infusion–related event (e.g., headache), the infusion rate should be reduced to half the rate being given at the time of onset of the event (e.g., from 50 mL/hr to 25 mL/hr or from 100 mL/hr to 50 mL/hr). Once the event has resolved, the investigator should wait for 30 minutes while delivering the infusion at the reduced rate. If tolerated, the infusion rate may then be increased to the next closest rate on the patient's infusion schedule and the rate increments resumed.

### Severe Infusion-Related Reactions

Patients who experience a severe infusion–related event (Grade 3) or a complex of flushing, fever, and throat pain symptoms should have their infusion interrupted immediately and should receive aggressive symptomatic treatment. The infusion should be restarted only after all the symptoms have disappeared. The initial infusion rate at restart should be half of the infusion rate that was in progress at the time of onset of the reaction.

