# **Managing Infusion-Related Reactions**

Infusion of ocrelizumab is administered under the close supervision of an experienced healthcare professional with access to appropriate medical support to manage severe reactions such as serious IRRs.

Patients who experience severe pulmonary events, such as bronchospasm or asthma exacerbation, must have their infusion interrupted immediately and permanently. After administering symptomatic treatment, monitor the patient until the pulmonary symptoms have resolved because initial improvement of clinical symptoms could be followed by deterioration.

Because transient hypotension may occur during ocrelizumab infusion, patients with low blood pressure should be monitored carefully. Patients with a history of congestive heart failure (New York Heart Association Class III/IV) were not studied.

In case of IRRs during any infusion, see recommendations in Section 4.3.4.

In the event of a suspected anaphylactic reaction during study treatment infusion, please refer to Appendix 6.

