# 5.1.2.4 Hypersensitivity Reactions

Hypersensitivity may be difficult to distinguish from IRRs in terms of symptoms. A hypersensitivity reaction may present during any infusion, although not typically during the first infusion. For subsequent infusions, more severe symptoms than previously experienced, or new severe symptoms, should prompt consideration of a potential hypersensitivity reaction. If a hypersensitivity reaction is suspected during an infusion, the infusion must be stopped immediately and permanently. Patients with known IgE–mediated hypersensitivity to ocrelizumab must not be treated.

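### The Grade 3 infusion-reaction rule in Section 4.3.4.2 allows a restart after severe pulmonary events, for which Section 5.1.1.1 requires a permanent stop

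*Combined protocol and SAP*

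**What the plan says.** Section 4.3.4.2 sets the bedside rules: "Handling of IRRs will depend on the intensity of symptoms". For Grade 1 or 2, "the infusion rate should be reduced to half the rate being given at the time of onset of the event", with later re-escalation if tolerated. For Grade 3, or for a combination of flushing, fever and throat pain, the infusion is interrupted and symptoms are treated. Then: "The infusion should be restarted only after all the symptoms have disappeared". The next sentence sets the restart rate at half the rate in use at onset. For Grade 4, ocrelizumab is stopped and permanently discontinued; acute hypersensitivity and acute respiratory distress syndrome are the examples given.

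Section 4.3.4.1 mentions airway symptoms, but only as something to treat: "In patients with associated respiratory symptoms (stridor, wheeze, or bronchospasm), additional treatment with bronchodilators may be indicated".

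Section 5 adds two rules that are not tied to that ladder. Under Managing Infusion-Related Reactions in Section 5.1.1.1: "Patients who experience severe pulmonary events, such as bronchospasm or asthma exacerbation, must have their infusion interrupted immediately and permanently". The same subsection later says: "In case of IRRs during any infusion, see recommendations in Section 4.3.4". In Section 5.1.2.4: "If a hypersensitivity reaction is suspected during an infusion, the infusion must be stopped immediately and permanently".

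**The concern.** The Grade 3 paragraph covers every severe infusion reaction, so a severe bronchospasm falls within it. A nurse or physician working from Section 4.3.4.2 could treat the child, wait for symptoms to clear and resume at half rate. Section 5.1.1.1 forbids resuming. Section 5.1.1.1 also gives a reason for caution: after initial improvement the patient may deteriorate again. Clearing of symptoms is exactly the condition on which Section 4.3.4.2 allows a restart.

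At stake is the safety of children in what Section 1.3 describes as the first trial of ocrelizumab in paediatric patients. Section 4.3.4.2 is also likely to be used. Infusion reactions were the most common adverse event in ocrelizumab-treated adults, with an incidence of 34.3% in the relapsing MS trials (Section 1.2.4.2).

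**Working it through.** The point is a comparison of instructions. The plan gives no figure to reproduce, and no event rate from which a risk could be computed.

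**Step 1: apply both sets of rules to the same event.**

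| Event | Section 4.3.4.2 | Section 5 | Same action? |
|---|---|---|---|
| Severe (Grade 3) bronchospasm or asthma exacerbation | Interrupt, treat, restart at half rate once clear | Permanent stop (5.1.1.1) | No |
| Suspected hypersensitivity, Grade 3 | As above, if handled as an infusion reaction | Permanent stop (5.1.2.4) | No |
| Suspected hypersensitivity, Grade 1 or 2 | Halve the rate and continue, if handled as an infusion reaction | Permanent stop (5.1.2.4) | No |
| Either event at Grade 4 | Stop and discontinue permanently | Permanent stop | Yes |

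The first row is unconditional once severe is read as including Grade 3, which is how the subsection heading in 4.3.4.2 uses the word. The second and third rows depend on the reaction still being managed as an infusion reaction when hypersensitivity is suspected.

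**Step 2: follow the cross-references.** Section 4.3.4.2 refers only to the grading scale in Section 5.3.3, not to 5.1.1.1 or 5.1.2.4. Section 5.1.1.1 sends staff to 4.3.4, where the pulmonary exception is absent. Section 5.1.1.1 also warns that infusion reactions may not be clinically separable from acute hypersensitivity, but its pointer there is to 5.1.1.2, which is Infections. The hypersensitivity rule is in 5.1.2.4.

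**Step 3: check the other safeguards.**
- Sections 4.3.6 and 4.6.1 bar further treatment after a severe allergic or anaphylactic reaction. Neither lists pulmonary events, and 4.3.6 is checked before later doses, so it does not govern resuming the same bag.
- Appendix 6 stops the infusion for suspected anaphylaxis only.
- Section 4.3.2.3 requires the whole bag to be given unless a reaction makes discontinuation necessary. Within 4.3.4.2 only Grade 4 is said to do so.

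What remains uncovered is a Grade 3 pulmonary event, and suspected hypersensitivity that has not been judged Grade 4, severe or anaphylactic.

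**Step 4: count the occasions.** Dose 1 is two infusions. Single infusions follow every 24 weeks from Week 24 to Week 264: 264 / 24 = 11. A patient who completes treatment without extra split doses therefore has 2 + 11 = 13 infusions at which the rules could apply. This counts opportunities, not expected events.

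**The case against.** The best defence is that the texts can be reconciled. Section 5.1.1.1 is specific and mandatory. Section 4.3.4.2 is general, uses should, and calls itself guidance. Making resolution of symptoms a precondition for restart does not order a restart. The pointer to Section 4.3.4 comes after the permanent-stop sentence, so anyone following it has already met the specific rule. A physician must be available on site. All of this is fair, and an investigator with both sections in mind would stop. But the protocol sets no order of precedence. The sentence after the precondition gives the restart rate, so restart is the expected path, and the whole-bag requirement is itself mandatory. Someone who opens Section 4.3.4.2 during a reaction may not have read Section 5.1.1.1.

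On hypersensitivity the defence is stronger. It is a separately listed risk with its own clear rule, so a suspected case arguably leaves the infusion-reaction ladder altogether. That is why this half is secondary. It does not vanish, because the protocol itself says the two are hard to tell apart and its pointer to the rule is wrong.

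A reader might also infer two stronger points that the documents do not support:
- That Section 4.3.4.2 works purely by grade and ignores hypersensitivity. It has one symptom-based trigger (flushing, fever and throat pain, leading to the same restart rule), and its Grade 4 paragraph names acute hypersensitivity.
- That a Grade 2 reaction following a Grade 1 reaction at an earlier infusion puts the sections in conflict. Section 5.1.2.4 says: "For subsequent infusions, more severe symptoms than previously experienced, or new severe symptoms, should prompt consideration of a potential hypersensitivity reaction". That asks only for consideration. An investigator may consider hypersensitivity, reject it and slow the infusion, complying with both sections.

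**Conclusion.** The conflict is real. As written, the Grade 3 rule permits an action after a severe pulmonary event that Section 5.1.1.1 prohibits. The hypersensitivity gap below Grade 4 is genuine but lesser.

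The size is not quantifiable from the documents. Adult infusion reactions were mostly mild to moderate and most frequent at the first infusion, and no rate is given for Grade 3 pulmonary events or suspected hypersensitivity. No inference that children have been or will be harmed at any particular rate is supported.

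The conclusion rests on two readings: that severe in Section 5.1.1.1 includes Grade 3, and that Section 5.1.2.4, which mentions no grade, applies at any grade. The sponsor's intention is clear in Section 5, so this is an omission in the operational section and not a dispute about medical policy. It should be corrected.

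**What to change.** Add one sentence to the opening of Section 4.3.4.2 and repeat it in the Grade 3 paragraph:

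*Exception: for a severe pulmonary event such as bronchospasm or asthma exacerbation (Section 5.1.1.1), or whenever a hypersensitivity reaction is suspected (Section 5.1.2.4), stop the infusion immediately and do not restart it; the rate-reduction and restart rules do not apply.*

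Refer to this exception after the bronchodilator sentence in Section 4.3.4.1. As a clerical item, correct the hypersensitivity pointer in Section 5.1.1.1 from 5.1.1.2 to 5.1.2.4.

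The cost is one sentence in two places, two cross-reference edits in the next amendment, and a communication to sites. The sentence only carries existing Section 5 rules into the section used during infusions. It does not settle whether a patient with a severe pulmonary event may receive later doses. Sections 4.3.6 and 4.6.1 do not list such events, and the sponsor could state its position in the same amendment.

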## Life-Threatening Infusion-Related Reactions

Immediately stop ocrelizumab if there are signs of a life-threatening or disabling infusion-related event (Grade 4) during an infusion, such as acute hypersensitivity or acute respiratory distress syndrome. The patient should receive appropriate treatment (including use of resuscitation medications and equipment that must be available and used as clinically indicated). Permanently discontinue ocrelizumab in these patients who should be withdrawn from treatment and should enter the SFU period.

# 4.3.5 Delayed Dosing

If a scheduled dosing visit cannot occur within the time window or if an infusion cannot be administered as planned, a delayed dosing visit should be scheduled as soon as possible. To ensure that patients meet re-treatment criteria (Section 4.3.6), an unscheduled site visit (or unscheduled MN visit) should be scheduled within 2 weeks in advance of that delayed dosing visit.

The treating investigator must verify that all re-treatment criteria (Section 4.3.6), including safety laboratory parameters, are met before proceeding with the infusion of ocrelizumab. Any repeat laboratory tests must be performed, analyzed, and reviewed before administration of ocrelizumab.

Ocrelizumab should not be administered to patients with an active infection. Patients who develop infection following ocrelizumab administration should be promptly evaluated and treated appropriately. The subsequent infusion should be delayed until the infection has completely resolved and treatment with any anti–infective medications has been completed. Receipt of further ocrelizumab infusions is at the discretion of the investigator.

If the delayed dosing visit occurs more than 4 weeks from a scheduled dosing, the dose should be administered as two infusions of half the dose 14 days apart to mitigate the risk and severity of IRRs (see Section 4.3.2.3).

It is recommended that delayed infusions be administered in the morning, as patients should remain under observation for at least 1 hour after the completion of the infusion and up to 24 hours at the treating investigator's discretion.

# 4.3.6 Criteria for Re-Treatment with Ocrelizumab

A re-evaluation of the benefit-risk of continuing study treatment by the treating investigator must be performed for each patient at the end of the first 24 weeks and prior to any further dosing, and therapy continuation will only be granted to those patients where the benefit-risk is considered to be favorable.

A visit within 2 weeks prior to any dosing visit (i.e., scheduled dosing visit or delayed dosing visit) will be required to collect blood samples and patient information to enable the treating investigator to assess whether a patient meets re-treatment criteria at the time of an infusion with study drug.

Treating investigator must ensure he or she has reviewed the laboratory results of the patient prior to re-treatment with ocrelizumab. Any repeat laboratory tests must be performed, analyzed, and reviewed before administration of ocrelizumab.

Prior to re-treatment, the following conditions must be met:

- Absence of life-threatening (Grade 4) infusion-related event that occurred during a previous ocrelizumab infusion
- Absence of severe allergic or anaphylactic reaction to an ocrelizumab infusion
- Absence of active infection regardless of the grade (including active tuberculosis [TB] infection, either new onset or reactivation) and treatment with any anti-infective medications has been completed (see Section 5.1.1.2)

A patient with active TB infection or a Grade 3 infection must suspend ocrelizumab treatment for as long as needed to ensure full resolution of the infection.

The patient should receive medical care in adherence with local/national requirements until complete resolution of the infection and should be monitored subsequently as per local medical plans. Upon resolution of the infection and based on individual benefit-risk assessments, the patient will have the opportunity to restart ocrelizumab treatment if it is considered beneficial for him or her. Otherwise, the treating investigator can decide to permanently stop ocrelizumab.

- Absence of any significant or uncontrolled medical condition or treatment-emergent, clinically significant, laboratory abnormality
- ANC  $\geq 1.5 \times 10^{3}/\mu L$
- CD4 levels:
  - For children and adolescents: percent CD4  $\geq$  25%
  - For patients  $\geq$  18 years of age, the adult reference applies: CD4 cell count  $\geq$  250/ $\mu L$
- IgG Level:
  - For children and adolescents:  $IgG \ge 4.6 g/L$
  - For patients  $\geq$  18 years of age, the adult reference applies: IgG  $\geq$  3.3 g/L

Ocrelizumab—F. Hoffmann-La Roche Ltd 62/Protocol WA39085, Version 10

- No initiation of protocol–prohibited medications
- Body weight  $\geq$  25 kg
- Absence of ongoing pregnancy or positive pregnancy test or breastfeeding (for female patients)

In the event of pregnancy, the investigator must counsel the patient as to the risks of continuing with the pregnancy and the possible effects on the fetus. Given that there are insufficient, well–controlled data from studies testing the use of ocrelizumab in pregnant or breastfeeding women, all infusions of ocrelizumab must be suspended until the completion of pregnancy and breastfeeding. Pregnant and breastfeeding patients should continue to follow the schedule of assessments for the study; however, no infusions of ocrelizumab will occur. If there is a concern with the ability of a pregnant or breastfeeding patient to perform all scheduled assessments, the investigator must contact the Medical Monitor for further discussion. Re–start of ocrelizumab treatment following pregnancy and breastfeeding will be decided as a result of a thorough benefit-risk discussion between the patient and investigator.

If any of these conditions are not met prior to re-dosing, further administration of ocrelizumab will be suspended (paused) until resolved or held indefinitely (see Section 4.6.1).

A patient experiencing a life-threatening (Grade 4) infection will be permanently discontinued from ocrelizumab treatment and will enter the safety follow-up period (see Section 4.6.1).

Any critical laboratory values will be provided to the treating investigator and the Medical Monitor. Investigators notified of their patient's critical laboratory test result will be instructed to suspend further treatment with study drug until the patient can be further evaluated. A repeat laboratory test may be necessary to confirm the results. Patients with critical values should not be re-treated until the re-treatment criteria are met and these laboratory values have normalized.

See also Section 5.3.5.6 for reporting of abnormal laboratory values.

### 4.3.7 Investigational Medicinal Product Accountability

All IMPs required for completion of this study (ocrelizumab) will be provided by the Sponsor where required by local health authority regulations. The study site will acknowledge receipt of IMPs using the IWRS to confirm the shipment condition and content. Any damaged shipments will be replaced.

Temperature conditions for all IMPs will be monitored during transit, and any discrepancies will be reported and resolved before use of the IMPs. All IMPs must be stored in a secure, environmentally controlled, and monitored (manual or automated)

area in accordance with the labeled storage conditions, with access limited to the investigator and authorized staff.

IMPs either will be disposed of at the study site according to the study site's institutional standard operating procedure or will be returned to the Sponsor with the appropriate documentation. The site's method of IMP destruction must be agreed to by the Sponsor. The site must obtain written authorization from the Sponsor before any IMP is destroyed, and IMP destruction must be documented on the appropriate form.

Accurate records of all IMPs received at, dispensed from, returned to, and disposed of by the study site should be recorded on the Drug Inventory Log.

# 4.3.8 Continued Access to Ocrelizumab

Currently, the Sponsor does not have any plans to provide Sponsor study drug (ocrelizumab) or any other study treatments or interventions to patients who have completed the study. The Sponsor may evaluate whether to continue providing ocrelizumab in accordance with the Roche Global Policy on Continued Access to Investigational Medicinal Product, available at the following website:

http://www.roche.com/policy\_continued\_access\_to\_investigational\_medicines.pdf

However, until the benefits/risks of ocrelizumab in children and adolescents have been fully assessed in a Phase III study, continued access to ocrelizumab will be evaluated cautiously by the Sponsor on an individual basis.

# 4.4 CONCOMITANT THERAPY

Concomitant therapy consists of any medication (e.g., prescription drugs, over-the-counter drugs, vaccines, herbal or homeopathic remedies, nutritional supplements) used by a patient in addition to protocol-mandated treatment from screening to the study completion/ discontinuation visit. All such medications should be reported to the investigator and recorded on the Concomitant Medications eCRF.

Concomitant medications will be reported at each visit in the relevant eCRFs starting from the baseline visit (including medication taken between screening and baseline). Any medications taken for the treatment of MS and any medications taken for the symptoms of MS prior to the baseline visit will be recorded at the baseline visit. Additionally, medications administered for any non–MS condition within 12 months prior to the baseline visit will also be recorded at the baseline visit.

